1.0 BACKGROUND

1.1 Introduction and Context

Tobacco use causes more than 7 million deaths per year worldwide (WHO, 2022) and continues to be the leading modifiable risk factor for cancer globally (Tran et al., 2022). In the United States, it remains the single largest preventable cause of disease, disability, and premature death with an estimated life expectancy of 10 years shorter than that of a non-smoker. Unfortunately, in the year 2020, 12.5% of U.S. adults (30.8 million people) continue to smoke cigarettes (CDC, 2022 Aug) despite the multiple smoking cessation treatments available. While the forms of tobacco use are changing, such as the increasing use of e-cigarettes, a 2019 study showed cigarettes remain the most commonly used tobacco product (CDC, 2020).

Among individuals who currently smoke cigarettes, over 2/3 (68%) have reported a desire to quit (CDC, 2022 Mar). In 2018, 55.1% of smokers reported making at least one quit attempt in the past year, however, only 7.5% of people who tried to quit succeeded (CDC, 2022 Mar). Overall, those who use smoking cessation therapies, such as counseling and medications, had a higher success rate than those who did not. For example, abstinence rates were 15% in people who used assistance versus 7% in those who did not at 12 month follow up (Shu-Hong, 2000), however, the rate of sustained abstinence continues to be low (Babb et al., 2017). While the proven benefit of both non-pharmacological and pharmacological therapy in many patients is encouraging, there is a need for additional treatments.

1.2 Current treatment for smoking cessation

There have been many studies showing the benefit of pharmacologic treatment in the assistance of smoking cessation. While the proportion of smokers who benefit from smoking cessation medications decreases during the first year of use, a net benefit remains at 12 months. Specifically, a meta-analysis reported an abstinence rate of 20% in people who attempted smoking cessation with medications versus 11% without medications at 12 months (Rosen et al., 2018). Common medications studied include nicotine replacement therapy (NRT), varenicline, and certain antidepressants. These medications have a variety of mechanisms proposed to treat the associated nicotine dependence of cigarette smoking. Varenicline is classified as a selective nicotinic receptor partial agonist, a pathway thought to affect the release of dopamine in the midbrain. A meta-analysis showed varenicline having a two- to threefold increase chance of successful long-term smoking cessation compared with pharmacologically unassisted quit attempts (Cahill et al., 2012). The most common antidepressant studied for smoking cessation is bupropion. Nortriptyline has also shown to be efficacious, however, serotonin reuptake inhibitors have not been shown to be helpful (Hughes et al., 2004). Bupropion has dopaminergic and noradrenergic activity while nortriptyline has relatively weak dopaminergic but significant noradrenergic activity. A Cochrane review showed bupropion doubles the odds of guitting smoking (Hughes et al., 2004). NRT replaces the form of nicotine by acting on the same nicotinic receptors as cigarettes, showing to be helpful when compared to no treatment. A Cochrane review reported NRT helps to increase the rate of quitting by 50-70% (Stead et al., 2012). When comparing these medications, there have been studies showing more participants guitting successfully with varenicline than with bupropion but limited studies comparing varenicline to NRT. There have been a small number of studies directly comparing bupropion with NRT with some heterogeneity but tend to favor bupropion (Hughes et al., 2004). This may suggest that if varenicline is more efficacious than bupropion, it may also more efficacious than NRT.

Behavioral treatments have also been shown to increase quit rates at 6 months even in the abstinence of pharmacotherapy. Specific interventions include, but are not limited to, motivational interviewing, CBT, and mindfulness-based therapy. A Cochrane review showed motivational interviewing resulted in improved quit rates when compared to brief advice (Lindson-Hawley et al., 2015). When looking at mindfulness-based therapy, a meta-analysis concluded it did not have a significant improvement in abstinence over other behavioral interventions (Maglione et al., 2017). A Cochrane review looking at

Page 5 of 22

various interventions showed benefit with any form of counseling (Hartmann-Boyce at al., 2021) and there has been no current consensus favoring one form of behavioral intervention. Additionally, when combining the results of studies in a meta-analysis, individual counseling compared to minimal intervention could increase the chance of quitting by 50-80% (Lancaster & Stead, 2017).

It is well established that pharmacotherapy and non-pharmacotherapy can both individually help with smoking cessation, however, combining pharmacotherapy and behavioral support has shown to further increase smoking cessation success (Patnode et al., 2021; Stead et al., 2016; Lancaster & Stead, 2017). Combined pharmacotherapy and behavioral intervention improved quit rates from an average of 8.6% in those receiving usual care to 15.2% (Patnode et al., 2021). While these interventions can have substantial clinical benefit, the rate of people who continue to smoke indicates a need for novel treatments.

1.3 Clinical trials for substance use and the rational for treatment with ketamine

Ketamine has shown early evidence of efficacy in the treatment of multiple types of substance use disorders. One study evaluating the adjunctive use of ketamine in heroin use disorder showed that a single-session of high-dose (2 mg/kg IM) ketamine demonstrated one-month abstinence rates of 85% compared to 55% abstinence in the low dose group (0.2 mg/kg IM), and one-year abstinence rates of 24% in the high dose group as compared to 6% in the low-dose control group (Krupitsky et al., 2002). In a follow-up study comparing three repeated sessions of ketamine infusions with concurrent psychotherapy to single-session treatment, abstinence rates were increased to 50% in the 3 session group as compared to the single session rate of 22% (Krupitsky et al., 2007). Related studies found that ketamine is useful as an adjunct to psychotherapy in the treatment of alcohol use disorder (Krupitsky & Grinenko, 1997) with one-year complete abstinence rates of 65.8% in the ketamine-assisted psychotherapy group compared to 24% in the control psychotherapy group. Additionally, motivational enhancement therapy combined with just one ketamine infusion was shown to improve likelihood of abstinence from alcohol when compared to midazolam (Dakwar et al., 2020). Ketamine has also been studied in cocaine use disorder and found to improve levels of motivation to guit using and reduce cocaine craving (Dakwar et al., 2014) as well as reduce rates of cocaine self-administration by 67% relative to baseline (Dakwar et al., 2017). When ketamine was combined with mindfulness-based relapse prevention therapy for cocaine use disorder, it was shown that 48% of subjects who had the addition of one ketamine infusion were abstinent after 2 weeks compared to 10% of those who received a midazolam infusion (Dakwar et al., 2019). The benefit of ketamine treatment across several different substance use disorders as well as the synergistic effect of adding ketamine to various methods of psychotherapy suggests there may be an underlying mechanism and therefore a role for ketamine in the treatment of other substance use disorders such as tobacco dependence.

1.4 The neurobiology of tobacco use dependence

While there are about 9000 chemicals in cigarette smoke, nicotine is the major psychoactive ingredient and the component most associated with tobacco dependence. There are multiple proposed underlying mechanisms leading to nicotine dependence that current smoking cessation medications have targeted, including both the sensitization of nicotinic receptors in the ventral tegmentum area (VTA) after a period of abstinence as well as conditioned stimuli throughout the day after the nicotinic receptors have been desensitized (Fagerström & Balfour, 2006). The main areas of study have involved the mesocorticolimbic dopamine system, specifically the VTA projecting to the nucleus accumbens (NAc). Nicotine stimulates the mesocorticolimbic dopamine system via nicotinic acetylcholine receptors in the VTA causing increased firing of dopamine in the NAc (Mahajan et al., 2021). However, preclinical studies have also shown other critical interactions contributing to nicotine dependence with influences not only of dopamine and acetylcholine but also glutamate and GABA in the limbic system, prefrontal cortex, amygdala, and hippocampus (Markou, 2008). There is also another neurobiological pathway thought to be involved in aversive processing and nicotine withdrawal. This consists of the projection from the medial habenula to the interpeduncular nucleus with major neurotransmitters being acetylcholine, glutamate, and substance P and could potentially have a role in limiting drug intake (Fowler et al., 2019). Furthermore, tobacco smokers have shown to have both structural and functional connectivity changes within the brain. For example, smoking can reduce gray matter volume in the orbitofrontal circuit (Li et al., 2015) and nicotine can temporarily increase fMRI signal in the striato-thalamo-orbitofrontal circuit (Bruijnzeel et al., 2015). The underlying mechanisms of these changes are multifactorial and likely involve multiple frontal-cortical inhibitory and excitatory balancing systems involved in nicotine dependence. While there has been past focus on the development of smoking cessation medications targeting the nicotinic system and dopaminergic system, the complexity of nicotine dependence shows there are other potential neurobiological targets for pharmacologic intervention.

1.5 Innovation and Importance of the Current Study

There are promising results in past studies of ketamine in the treatment of other substance use disorders (Krupitsky et al., 2002; Krupitsky et al., 2007; Dakwar et al., 2014; Dakwar et al., 2017). Given these studies, the neurobiological similarity between various substance use disorders (Uhl et al., 2019), and the potential influences of ketamine on the underlying neurological circuitry (Ezquerra-Romano et al., 2018), it would be beneficial to assess the role of ketamine in nicotine dependence. There has been one animal study showing reduction of nicotine self-administration in rats given ketamine, suggesting there may be an underlying mechanism of ketamine helpful in reducing nicotine use (Rezvani et al., 2018), however, there are currently no past studies in humans studying the effects of ketamine on smoking cessation.

2.0 PURPOSE/SPECIFIC AIMS

2.2 Purpose and Objectives of the Study

The primary objective of the proposed study is to preliminarily explore the feasibility, efficacy, and tolerability of ketamine in the treatment of tobacco use disorder associated with cigarette use. We seek to enroll 8 individuals with tobacco use disorder who use cigarettes.

2.3 Specific Aims

To achieve these objectives, the following Specific Aims are proposed:

- **Specific Aim 1:** To assess the feasibility of using ketamine-assisted brief motivational enhancement therapy in the treatment of cigarette smoking cessation
- **Specific Aim 2:** To preliminarily explore the efficacy, safety, and tolerability of ketamineassisted brief motivational enhancement therapy for smoking cessation

3.0 STUDY DESIGN/METHODS

3.1 Study Overview

This is an open label trial of ketamine-assisted psychotherapy to assess the efficacy and safety of weekly intramuscular injections of ketamine in the assistance of smoking cessation. This will be determined by evaluating the severity of craving as well as the number of cigarettes smoked the week prior to each session and at each follow up.

Subjects will participate in a baseline visit to complete informed consent as well as complete assessments to evaluate study eligibility and collect baseline data. Eligible participants will return for the initial ketamine intervention procedure. Participants will be subsequently monitored until they have returned to baseline based on clinical assessment during which time they will complete measures assessing their perception of the interventional experience.

3.2 Duration of Intervention and Study

Participants will complete a total of 6 study visits (including baseline assessment and follow-up assessments) as shown in **Table 1**. Medication sessions with intramuscular ketamine will occur weekly for three weeks. Participants will meet virtually or in person for follow-up at 4 and 8 weeks following final medication session.

3.3 Description of Assessments

For full description of assessments, see exploratory outcomes (section 6.3).

3.4 Schedule of Assessments

The instruments to be used are standardized, have good psychometric properties, and are widely used. The schedule of study assessments is provided in **Table 1**.

Page 8 of 22

Table 1: Schedule of Assessments

	Purpose	TIME POINT						
Instrument Name		BL	Tx 1-3	Follow-up				
		(Wk 0)	(Wk 1-3)	(Wk 4, 8)				
Self-Reports and Consents								
Informed Consent	Obtain informed consent	Х						
Demographics Form	Sample characterization	Х						
General Anxiety Disorder (GAD-7)	Self-report of anxiety symptom severity	х	х	Х				
Insomnia Severity Index (ISI)	Measure of insomnia severity	Х	Х	Х				
Mystical Experiences Questionnaire (MEQ)	Measure of perceptual experiences	Х	х	Х				
Five Facets of Mindfulness (FFMQ)	Assess aspects of mindfulness related	Х	Х	Х				
Fagerstrom Test of Nicotine Dependence (FTND)	Measure of nicotine dependence	х	х	Х				
Questionnaire on Smoking Urges (QSU)	Assessment of smoking cravings	х	х	Х				
Wisconsin Smoking Withdrawal Scale 2 (WSWS2)	Measures severity of smoking withdrawal	х	х	Х				
Timeline Follow- Back (TLFB)	Measure of substance use	Х	Х	Х				
Rhode Island Change Assessment (URICA)	Measure of stage of change	х	х	Х				
Beck Depression Inventory (BDI-II)	Self-report of depression symptom severity	X	×	X				
	Clinician Assess	ments						
History and Physical Exam	Eligibility assessment	Х						
Vital Signs Measurement	Obtain readings of blood pressure, pulse, temperature, respirations and pulse oximetry	Х	X*					
Pre-screening Questionnaire	To assess for basic eligibility criteria before completing a full baseline visit.	Х						

Page 9 of 22

Urine Pregnancy Test (female subjects only)	Eligibility assessment	х	Х	
Electrocardiogram (ECG; subjects with cardiac comorbidities or on QTc prolonging medications only)	Assessment of cardiac function	х		
Urine Drug Screen	Assess for use of psychoactive substances	Х		
Salivary cotinine level	Assessment of smoking status	Х	Х	Х

* Vital signs (blood pressure, pulse, respiratory rate, and pulse oximetry) will be obtained pre- and posttreatment. If there is an increase in systolic or diastolic blood pressure >30 mm Hg from baseline, or an increase in pulse rate >30 bpm from baseline, subjects will be treated with standard of care antihypertensive medications (i.e. clonidine) and the measurements will be repeated every 20 minutes until BP and pulse are within 30 points of the baseline values.

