3.5 Baseline Assessment Procedures

After completing study informed consent, participants will undergo a comprehensive evaluation to assess for inclusion and exclusion criteria. This will include self-reports and clinician assessments as shown in Table 1. The comprehensive exam will also include a history and physical exam by the study PI (pulse oximetry measurements will be a component of the respiratory evaluation) and baseline medication evaluation for potential harmful interactions. Urine pregnancy tests will be completed for every woman of childbearing potential at the initial assessment and prior to each treatment session. Urine drug screens will be completed for all participants at the initial assessment to detect use of recreational psychoactive substances other than nicotine. Saliva cotinine levels will be measured at baseline, prior to each ketamine session and at 3 month follow up to detect smoking over approximately the previous 6 days. An ECG will be performed in participants with QTc interval of 450ms or longer in males or 460ms in females being exclusionary.

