5.2 Inclusion Criteria

A subject may be eligible for enrollment if all the following inclusion criteria apply within the thirty days prior to first experimental session:

- 1. 21 to 65 years old.
- 2. Able to provide informed consent.
- 3. Be a daily cigarette smoker with multiple unsuccessful previous quit attempts, and report a continued desire to quit smoking.
- 4. Agree to abstain from smoking for the ketamine session from 1 hour before ketamine administration
- 5. Agree to refrain from using any psychoactive drugs, including alcoholic beverages, within 24 hours of ketamine administration. Exceptions include caffeine and nicotine.
- 6. Subjects taking other psychotropic medications must be maintained on a stable dose for at least four weeks before study initiation.
- 7. Be healthy as determined by screening for medical problems via a personal interview, a medical questionnaire, a physical examination, an electrocardiogram (ECG) to verify normal QTc intervals.
- Subjects with normal blood pressure not on antihypertensive medications or medication controlled hypertension as defined baseline visit systolic blood pressure (SBP) <140 mmHg or a diastolic blood pressure (DBP) <90 mmHg.

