will contact the participant immediately to assess concerns and assure participant safety. The PI will attempt to address all participant concerns and will set up an alternate referral for counseling for those who desire it from outside the project. All participants will review, at the initiation of participation, an informed consent document which specifically reviews potential psychological distress as a potential outcome of participation. If necessary, the participant will be asked to complete a safety plan and to call the project staff, a national hotline, or 911. The Mobile Crisis unit of Charleston County, which involves a team of police and psychiatric workers, or the EMS unit may be dispatched to the participant's home to assure safety. The investigative team has a long history of ensuring participant safety using similar methods in these populations.

Pre-Intervention Assessment: A comprehensive exam will be conducted as part of the baseline assessment to minimize risks from study participation. This will include assessment of anxiety severity. The comprehensive exam will also include a history and physical exam by the study PI (pulse oximetry measurements will be a component of the respiratory evaluation), baseline medication evaluation for potential harmful interactions, and electrocardiogram to ensure safe study participation.

Peri-Intervention Monitoring: Subjects will be continuously medically and psychiatrically monitored throughout the course of the intervention and until return to medical and psychiatric baseline. Subjects will be instructed not to eat for at least 2 hours before taking the intervention sessions to reduce the risk of nausea and vomiting. Emergency services will be contacted in the event of any medical complications. Subjects will not be allowed to drive themselves after the interventional visits, and alternative transportation will be arranged if needed.

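### Table 1 limits the baseline ECG to a subgroup, while inclusion criterion 7 and Section 9.0 require it without restriction, so a participant could be dosed with QTc unchecked.

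*Combined protocol and SAP*

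**What the plan says.** The protocol refers to the ECG or its findings in five places.

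- **Section 3.4, Table 1.** The row is labelled "Electrocardiogram (ECG; subjects with cardiac comorbidities or on QTc prolonging medications only" and is marked at baseline only.
- **Section 3.5.** Of the baseline evaluation it says "This will include self-reports and clinician assessments as shown in Table 1". Later it says "An ECG will be performed in participants with QTc interval of 450ms or longer in males or 460ms in females being exclusionary". This is the only place where the 450 and 460 ms limits appear.
- **Section 5.2, criterion 7.** Being healthy is to be established by screening that includes "an electrocardiogram (ECG) to verify normal QTc intervals". The lead-in makes all criteria mandatory and sets the window: "the following inclusion criteria apply within the thirty days prior to first experimental session".
- **Section 5.3, criterion 7.** A clinically significant ECG abnormality is exclusionary.
- **Section 9.0, Pre-Intervention Assessment.** The comprehensive exam includes "baseline medication evaluation for potential harmful interactions, and electrocardiogram to ensure safe study participation".

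Neither Section 5.2 nor Section 9.0 names a subgroup, and no text reconciles them with the Table 1 row.

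**The concern.** A schedule of assessments is what site staff usually work from when they order tests. Read literally, this one tells them not to order an ECG for a participant without a cardiac comorbidity or a QTc-prolonging drug. For that participant neither the normal-QTc criterion nor the 450/460 ms limits can be assessed, and an ECG abnormality the participant does not know about would not be found. The person could then receive up to three ketamine injections with a mandatory pre-dose criterion unverified. At stake are a safety check before dosing and the eligibility of those enrolled. The primary outcome, completion of treatment, is not affected.

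**Working it through.** The plan states no figure to reproduce. The check is a comparison of texts, followed by a simple count.

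**1. Who gets a baseline ECG under each section**

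| Place | Population |
|---|---|
| Table 1 | Cardiac comorbidity or QTc-prolonging drug only |
| Section 5.2, criterion 7 | No subgroup; all criteria must be met |
| Section 9.0 | No subgroup |
| Section 3.5 | Unclear; refers to Table 1 for assessments |

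**2. Can all of these be followed?** Take a daily smoker with no cardiac comorbidity and no QTc-prolonging drug. Table 1 gives no ECG. Criterion 7 needs one. Both cannot be satisfied.

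**3. Does Section 3.5 resolve it?** No. With a comma after the word participants, its sentence means an ECG for everyone, with the limits as exclusions. Without the comma it makes no sense, since QTc is known only after the ECG. It could also have lost a subgroup phrase. On any of these readings, Table 1 still conflicts with Sections 5.2 and 9.0.

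**4. Is the bracket a real limit?** It reads as one. An earlier row of Table 1, "Urine Pregnancy Test (female subjects only", uses the same form to restrict a test to part of the sample.

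**5. How many could be affected?** Inputs: about 8 participants (Section 5.4) and 3 weekly injections each (Section 3.2), so 8 x 3 = 24 planned doses. Let k be the number in the Table 1 subgroup. The documents do not give k, so the values below are assumptions.

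- Participants without a QTc check = 8 - k
- Doses without a QTc check = 3 x (8 - k)

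| k (assumed) | Participants | Doses of 24 |
|---|---|---|
| 0 | 8 | 24 |
| 2 | 6 | 18 |
| 4 | 4 | 12 |
| 6 | 2 | 6 |
| 8 | 0 | 0 |

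Under Sections 5.2 and 9.0 both counts are 0 whatever k is.

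**6. Where might k lie?** Two features pull in opposite directions. Exclusion criteria 6 and 7 remove cardiovascular disease, angina, uncontrolled hypertension and related conditions, so few people with cardiac comorbidities would remain. Inclusion criterion 6, however, admits people on stable psychotropic drugs ("Subjects taking other psychotropic medications must be maintained on a stable dose for at least four weeks before study initiation"), and some of those drugs may prolong QTc. The documents do not allow the range to be narrowed further.

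**The case against.** The strongest reply is that the eligibility criteria govern. Section 5.2 makes every inclusion criterion mandatory, Section 9.0 makes the PI responsible for assessing eligibility, and Section 14.0 has the PI or a co-investigator give the drug. Dosing without an ECG would breach Section 5.2, and a careful check would catch it. This stands as mitigation, and it makes the harm conditional. It does not remove the conflict, because the PI works from the same contradictory text and could take the ECG as not applicable.

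Other points have some force:

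- Those who would miss the ECG have no known cardiac comorbidity and take no QTc-prolonging drug, and the risk sections do not list QTc prolongation as a ketamine effect. What is shown is therefore an unverified criterion in a lower-risk group, not demonstrated injury.
- The bracket comparison is suggestive only. For the pregnancy test, Section 3.5 defines the population more narrowly than the table does, so the body text can refine a bracket.
- The dose count adds little beyond the participant count, because one baseline ECG is meant to cover all three injections.
- A targeted ECG may have been intended. In that case criterion 7 and Section 9.0 are wrong and need amending, so the protocol has to change either way.

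**Conclusion.** The concern holds. The Table 1 row contradicts inclusion criterion 7 and Section 9.0, and Section 3.5 leaves the conflict open. If staff follow the schedule, anywhere from 0 to 8 of the planned participants could start ketamine without a QTc check, depending on the unknown k; if they follow Section 5.2, none could. The conclusion about the text rests on no assumption. The size depends on k and on which section staff follow. A pre-dose safety criterion that cannot be applied consistently as written should be corrected before anyone is dosed, even in a study of about 8 people.

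**What to change.** Make two edits.

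1. In Table 1, remove the subgroup restriction from the ECG row, so that every participant has an ECG at baseline.
2. In Section 3.5, replace the ECG sentence with wording such as: *All participants have a baseline ECG; a QTc of at least 450 ms (males) or at least 460 ms (females) is a reason for exclusion.*

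Repeating the limits in Section 5.3 would be tidy but is optional.

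The alternative is to keep the subgroup and amend criterion 7 and Section 9.0 to match. That would also remove the contradiction, but it drops a safety check that two sections already state, so the universal ECG is the better choice.

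Beyond the wording, the cost relative to Table 1 is 8 - k extra ECGs among enrolled participants, at most about 8. Sections 5.2 and 9.0 already require all of them.
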